Recruitment of prospective participants is detailed in the recruitment section. In all cases, once contact is made with a prospective participant, study personnel will provide a brief synopsis of the study, including study purpose, study procedures, potential risks and benefits, compensation and right to withdrawal from the study at any time without penalty. If interested in participating, study personnel will administer a brief screening form to the participant to ensure eligibility criteria are met. If ineligible, the participant will be informed of the reason for ineligibility and screening information will be retained without the participant's identifiable information (name, birthdate, etc.). If eligible, the research personnel will complete informed consent with the maternal participant. This informed consent may be completed in-person on paper, or remotely with a member of the research staff via Zoom (or similar platform) with an e-signature. Maternal participants will provide permission/consent for their infants to participate in the study, as infant-specific data, including background birth information and infant measurements, will be collected and the intervention has the potential to affect infant health. In all cases, maternal participants will sign and receive a copy (either hard copy or electronic copy) of the informed consent document. Any paper original copies will be kept and filed by research personnel. A separate addendum informed consent will be obtained to video-record AME sessions for interrater reliability. After informed consent, participants will complete baseline study measures/surveys (in-person, over phone or remote video/Zoom, or emailed survey; assessing maternal/fetal health, maternal demographics, maternal mood, reproductive history, body image concerns, experiences of discrimination, etc; see questionnaires for specifics) and be randomized to a group via computer-generated permuted block randomization stratified by pre-pregnancy BMI status (overweight: 25-29.9 or obese: ≥30). Subjects will have a 1:1 chance of being randomized to either study group, as indicated in the consent document. Study participation will be documented in the maternal participant's electronic medical record to alert providers to study participation. Study staff will meet remotely or in-person with participants in both groups weekly from 37 to 40 weeks of gestation for delivery of the assigned intervention. To maximize participant convenience and safety of all involved (given new standards/recommendations around social distancing) study "visits"/contact points will have the potential to be conducted completely remotely via a secure video call (e.g., HIPAA-compliant Zoom call with screen sharing when needed), audio phone call, or emailed survey. When/if feasible, preferred, and safe according to University research standards and current county-level guidance/restrictions, visits may also involve in-person meetings between the study participant and study staff (though the experimental condition lactation consultants will always deliver the intervention remotely). In-person visits may occur at the hospital/clinics before/after a prenatal visit or another mutually agreed upon convenient, private place. The details of study visits, according to assigned intervention are detailed below. Experimental Condition (AME): With the assistance of study staff, who will facilitate all study visits, participants randomized to AME will complete a test video call at enrollment, if possible, with the telelactation provider who are available for on-demand, one-on-one visits, 24/7) to increase familiarity with the service prior to AME instruction. Note that for subsequent study visits, if for any reason an IBCLC is not available, the study may use a substitute remotely-based IBCLC who is trained in study procedures. Participants will be taught the AME technique at the 37 week study visit after first viewing an introductory video demonstrating the technique. At the visit, study staff will initiate a 3-way meeting/connection with an available, remote International Board-Certified Lactation Consultant (IBCLC) and the study participant if the visit is remote (e.g., Zoom video call). If the study visit is inperson, study staff will initiate remote 2-way connection between themselves and study participant with a remote IBCLC via a secure video platform (e.g., Zoom). After connecting, the remote IBCLC will provide video-based expert instruction and guided feedback on AME and milk collection as the participant engages in the technique. Note that IBCLCs are trained in hand-expression as a fundamental professional skill and will receive additional training and oversight by study personnel (see intervention fidelity below). For participants whose study visits are conducted completely remotely, these meetings will occur via a secure HIPAA-compliant platform like Zoom which allows study participant, study staff, and IBCLC to see/converse with each other simultaneously. This will require that participants use their own electronic device (e.g., smart phone, laptop) for the visit. These meetings will be scheduled a convenient time for the participant, IBCLC, and study staff. When a video-based remote connection is not possible or problematic (e.g., WiFi issues), study staff will initiate a 3-way audio only phone call instead with the IBCLC and participant, and hand expression education will occur over audio to the extent possible, with subsequent referral to supplementary streaming videos demonstrating hand expression. As per our pilot study protocol, AME will continue for a maximum of 10 minutes during study visits (participants will also be advised to do AME for no longer than 10 minutes during their independent practice between study sessions). For any in-person study visits, any milk output will be collected into study-provided containers and syringes and stored for future analyses as per the protocol outlined below (disposition of antenatal milk). During remote sessions, any AME milk that is collected may be labeled as milk that may be given to the study, and frozen by the participant. This milk may then be collected and aliquoted by study staff at a later date (e.g., no contact porch pick-up of milk at participant's home by study staff members). For all AME sessions, additional breastfeeding education will be provided by the IBCLC as requested by participant and documented by study staff. Study staff will facilitate the overall visit (e.g., introductions, provision of milk collection containers). IBCLCs will reinforce/provide feedback on AME technique at each weekly study visit until delivery, with a similar format to the initial visit. Around the time of the initial 37 week visit (this may be before or after the visit, dependent on mode of AME education delivery), study staff will provide participants oral and written instructions to continue AME 1-2 times/day at home until delivery. Instructions (reinforced in weekly visits) will also contain information on milk storage, transport to the hospital if participant is storing milk at home, and use; AME contraindications; and when and how to seek assistance for any problems (please see attached: brochures in "other" documents). Please note that for participants whose visits will occur remotely, members of study staff will drop off supplies for AME (e.g., collection containers, labels, syringes, refrigerator boxes for transport of milk to hospital) before the first scheduled visit, so that participants have supplies at the time of their first session. These will be done in accordance with any county standards in-place at the time (i.e., no-contact porch drop-off deliveries, PPE worn if any in-person contact). Compliance with home practice, including AME timing, milk volume obtained, and any problems, will be assessed from after the first study visit until delivery via daily web-based survey "diaries" (if participant declines web-based diaries or there are technical problems with web-based diaries, participants may be provided written diaries to be returned to study personnel at a time/place to be arranged, e.g., no contact porch pick up). Web-based survey diaries will be administered with an automated SMS notification sent daily to the participant with up to 3 reminders through the day to complete. The responses to web-based diaries will be automatically recorded in a secure Access study database; if participant completes written diaries, their answers will be manually entered in Access database by study staff. With regard to the SMS alert system for the web-based diaries, a two-way text messaging system has been built at the University and associated hospital for this purpose (as has the survey/diary system itself); the system utilizes a server

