pregnancy, either remotely or in-person, similar to those in the AME group. In-person visits may occur at the hospital/clinics or another private mutually-agreed upon location; remote visits will be via a secure remote platform, such as the University's HIPAA-compliant Zoom. Visits will be approximately 10 minutes, similar to the intervention group. In this time, participants will view a standard set of web-based videos addressing evidence-based infant care, unrelated to feeding/breastfeeding. Videos will focus on a different theme each week (e.g., safe sleep, car seat safety, managing crying/colic), downloaded from free and reputable patient education sites. If visit is remote, study staff will attempt to "screen share" videos so that we may verify that participant actually views/receives the intended education (rather than directing participant to view videos on their own). Data Collection and Procedures Unrelated to Intervention Delivery: We will collect EMR data regarding maternal pre-pregnancy body mass index (BMI) and gestational weight gain, maternal and infant health conditions, labor and delivery information, and hospital infant feeding practices from the antenatal and postpartum medical records. Prenatal, intrapartum, and postpartum EMR data is housed within the hospital data systems, which the study team will access via their research and clinical affiliation with the hospital after IRB approval. In the postpartum period, study measures (surveys) assessing breastfeeding practices, perceptions, problems, satisfaction, plans, and education/support, as well as maternal mood, birth experience, childcare plans and use, and maternal employment (see questionnaires), will be completed by participants in both groups at weeks 2, 6, and 12 weeks, and 6 and 12 months postpartum. These measures may be completed remotely via emailed survey, in recognition of the time constraints faced by new mothers in scheduling study visits and calls. When difficulties are encountered in electronic survey completion, we will call participants or, when feasible, meet them during regularly scheduled postpartum clinic visits to complete measures (or at another mutually agreed upon time/location). If a participant elects to complete postpartum measurements and collection of a milk sample, the survey may be completed in-person at that time, as well. A subset of participants will also have included into their Baseline and postpartum surveys questions on sexual dysfunction. Please note that this survey is necessarily concurrent with a specific timepoint, and so participants who have already completed their participation in the study will not be asked to retrospectively complete this survey. In fulfillment of Aim 3, we will conduct individual telephone interviews with $\approx 25\%$ of participants from both groups at 6 weeks postpartum, or earlier if they indicate that they discontinued breastfeeding at the 2 week postpartum survey or otherwise notify us at any point that they have decided to not start breastfeeding, do not initiate breastfeeding, or stop breastfeeding. We anticipate conducting interviews with approximately 70 participants, 35 from each group, selected purposively based on variability in AME uptake (e.g., some participants who did not complete any AME, some who did it once daily, twice daily, etc.), demographics, and current breastfeeding status to achieve a representative group). Interviews will continue until thematic saturation is reached (estimated at ≈25% of sample from our prior research). Interviews will address aspects of both AME and the control condition to maintain participant blinding to study purpose. Specifically, we will query participants on motivating factors for study participation; perceived benefits/utility of AME and antenatal video-based infant education; experiences with and evaluation of other breastfeeding and infant education support resources; experienced or anticipated burdens/challenges/drawbacks to AME and the control condition; and for AME participants, factors/contexts impacting AME uptake and use of antenatal-expressed milk, as well as suggested modifications to the AME intervention or study protocol. Interviews will be conducted by a qualitative research consultant or study personnel. Interviews will follow a semi-structured interview guide, adapted from our current AME pilot RCT, and may be modified as the study progresses based on themes raised in prior interviews or issues encountered by study personnel. Interviews are expected to last 30-45 minutes and will be audio-recorded and transcribed verbatim by QDAP, another secure (e.g., HIPAA compliant) transcription service, or study personnel. Both audio files and transcripts will be retained electronically without identifying information in accordance with IRB protocols.

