
STATISTICAL DESIGN AND POWER

Sample Size and Power

The total proposed enrollment of 280 women was determined considering a feasible rate of recruitment, expected effect size of the AME intervention on primary outcomes, testing of multiple hypotheses, and anticipated rate of attrition and protocol non-adherence at 2 weeks postpartum (primary outcome assessment). Our recent intervention research with normal weight and overweight/obese women demonstrates medium sized effects (standardized mean difference, d) for the AME intervention at 1-2 weeks postpartum compared to an education control in terms of higher levels of breastfeeding selfefficacy (AME: M=52.59, SD=9.92, Education: M=45.71, SD=15.71, d=0.53) and greater percentage of breast milk feeds (AME: M=89.50, SD=20.372; Education M=78.64, SD=27.303, d=0.45). Regarding exclusive breastfeeding at 1-2 weeks, rates of 0.27 have been reported among overweight/obese women.32 With a sample size of at least 210 (105 per group), we can detect with .80 power betweengroup differences in the proportions in breastfeeding exclusivity at 2 weeks postpartum as small as .172 (medium effect size of OR=2.55 using likelihood ratio chi-square statistics) at an adjusted test-wise significance level of .0167. While there is a fair amount of heterogeneity in the published effect sizes for breastfeeding support interventions among overweight and obese women and for AME specifically, our estimate lies in the range of reported effect sizes in the field. 12,32 While the examination of long-term efficacy of AME is more exploratory (Aim 2), we will be able to detect small to medium interaction effects between groups over time as small as f = .323 when using repeated measures F-tests with at least four postpartum outcome time points. Our pilot work and previous studies utilizing similar populations and recruitment sites indicate that we can conservatively anticipate combined study attrition and intervention dropout at ≈25%. To ensure 210 participants with complete follow-up to 2 weeks and no protocol deviations, we will enroll 280 women.

Statistical Methods

Preliminary Analyses: For Aims 1 and 2, detailed exploratory data analyses will first be performed, involving data description and data screening for anomalies (e.g., outliers, nonnormality, etc.). The results from this initial investigation will be used to: 1) describe

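### Aim 2 sensitivity statement: the small-to-medium label and the limit f = .323 do not agree, the figure cannot be reproduced from what is stated, and the documents do not show which is wrong

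*Combined protocol and SAP*

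**What the plan says.** The statement is in the combined protocol and SAP under Sample Size and Power. After describing Aim 2 as more exploratory, it says "we will be able to detect small to medium interaction effects between groups over time as small as f = .323". The method named for this is an F-test for repeated measures, and the assumed number of measurement occasions after birth is four or more. It is the only sensitivity statement given for Aim 2.

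The nearby inputs belong to another calculation. For exclusive breastfeeding at 2 weeks the plan says "With a sample size of at least 210 (105 per group), we can detect with .80 power" and tests "at an adjusted test-wise significance level of .0167". Neither the sample size, the power nor the alpha is repeated for the Aim 2 figure. The 210 is defined as women with complete follow-up to 2 weeks and no protocol deviations.

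The data-collection text schedules five postpartum surveys, which "will be completed by participants in both groups at weeks 2, 6, and 12 weeks, and 6 and 12 months postpartum". Four or five waves are therefore both consistent with the power statement. Allocation is equal: "Subjects will have a 1:1 chance of being randomized to either study group".

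**The concern.** A minimum detectable effect is a floor. If the floor is f = .323, the design does not reach small effects at the target power, and it does not reach a medium effect of .25 either. If the design does reach small-to-medium interactions, the floor must be lower than .323. The sentence claims both.

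The time-by-treatment interaction is a term in the planned model for every repeatedly measured outcome. A reader faced with a non-significant interaction would turn to this sentence to judge which effects the trial could have seen. The label and the number give that reader different answers.

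**Working it through.** **Inputs.** N = 210 in total, 105 per arm, and power .80 (both stated for the 2-week outcome and assumed to carry over). Waves m = 4 or 5. Alpha is not stated for Aim 2, so .05 and .0167 were both tried. Correlation ρ is not stated, so 0 to .7 was tried. No sphericity correction unless noted.

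**Label against number.** On the usual benchmarks, .25 < .323 < .40. The midpoint of medium and large is (.25 + .40)/2 = .325, so .323 is almost exactly midway.

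**Attempt to reproduce .323.** For numerator df m − 1, find the noncentrality λ that gives power .80 under the noncentral F, then convert to f.

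*Convention A:* λ = N·f², so f = √(λ/210).

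| alpha | waves | df | λ | limit f | power at f = .25 |
|---|---|---|---|---|---|
| .05 | 4 | 3, 624 | 10.971 | .229 | .872 |
| .05 | 5 | 4, 832 | 12.004 | .239 | .839 |
| .0167 | 4 | 3, 624 | 14.159 | .260 | .761 |
| .0167 | 5 | 4, 832 | 15.373 | .271 | .713 |

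With the multivariate denominator df (206 or 205) the limits hardly move: .230, .241, .262 and .274. The lowest power at f = .25 is then .70.

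*Convention B (univariate):* λ = N·m·f²/(1 − ρ), so f = √(λ(1 − ρ)/(210m)). At alpha .05 with 4 waves, ρ = 0 gives √(10.971/840) = .114, and ρ = .7 gives √(10.971 × .3/840) = .063. Over both alphas and both wave counts the range is about .06 to .13. Power at f = .25 exceeds .99 throughout.

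No setting in A or B returns .323. The printed figure is between .323/.274 = 1.18 and .323/.229 = 1.41 times the limits under A, and well over twice those under B.

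**Inputs that do land near .323.**
- Per-arm n in place of total N: √(10.971/105) = .323 at alpha .05 with 4 waves. With the df also based on 105 women it is .324 to .329.
- Total N of 140, alpha .0167, 4 waves, multivariate df: λ = 14.583 and √(14.583/140) = .323.
- N = 210 with a sphericity correction: alpha .025, 4 waves, ε = .5 and λ = (N − 2)·f²·ε give .321.

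These routes differ in kind. The first points to a scaling slip, and the other two to a correct number with a wrong label. All were found by searching for a match, so none identifies the cause.

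**If .323 is the true .80-power limit on the usual scale.** λ at f = .25 is then (.25/.323)² = .0625/.1043 = .599 of the λ needed. At alpha .05 with 4 waves that is 10.971 × .599 = 6.57, giving power .557 (.550 with 5 waves). At alpha .0167 it is .514 (.506 with 5 waves). At f = .10 power would be .11 to .12 at alpha .05 and about .06 at .0167.

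**The case against.** A reader might infer from the last calculation that Aim 2 has only a 51 to 56% chance of detecting a medium interaction. The documents do not support that as a finding. It holds only if .323 is the true limit on the scale where .25 is medium. With 210 women and no sphericity correction, power at f = .25 is 70% to over 99%. The figure can only be given as a conditional.

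A second tempting step is to strike the small-effects claim whatever the rerun shows. That also goes too far: the univariate limits of about .06 to .13 bracket the small benchmark of .10, and a limit near .23 would fairly be called small to medium.

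A third is to argue from the plan's own usage. It says its earlier work "demonstrates medium sized effects (standardized mean difference, d) for the AME intervention at 1-2 weeks postpartum", with d = 0.45 and 0.53, and f = d/2 would put those at .225 and .265. But that identity is for a two-group difference at one time point. It does not carry over cleanly to an interaction with 3 or 4 df and an undefined f, so the point does not rest on it.

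The stakes are also limited. Aim 2 is described as more exploratory, its outcomes are secondary, the sample size is justified by the 2-week outcomes, and the Statistical Methods section promises point and interval estimates for each comparison. All of this stands and lowers the severity. It does not remove the contradiction within the sentence.

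**Conclusion.** The point holds in limited form. The sentence is internally inconsistent on the usual benchmarks for f, and .323 does not reproduce at .80 power with 210 women and four or five waves under either uncorrected F convention. Those conventions give about .23 to .27 or about .06 to .13.

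The documents do not show whether the number or the label is at fault, nor how the number arose. They do not establish that the long-term aim has low power. The recomputed limits assume that the 210 women and .80 power carry over from the primary outcome. The 210 is secured only to 2 weeks, so loss between then and 12 months would raise the limits. Severity: minor.

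**What to change.** Rerun the calculation and state its inputs: alpha, power, F convention and definition of f, within-person correlation, sphericity assumption, number of waves, and an N that reflects expected retention at the later time points. Then rewrite the sentence so that number and label agree.

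- If .323 is confirmed on the usual scale, relabel the range as medium to large and add that power at f = .25 would be about .51 to .56.
- If the limit is lower, print that value and keep the small-to-medium wording only where the new limit supports it.

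The cost is one sentence and a short recalculation. The stated sensitivity of an exploratory aim may read less favourably. Enrolment and data collection do not change.

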univariate and bivariate data distributions; 2) identify imbalances between treatment groups and associations between the dependent variables and suspected covariates/confounders; 3) evaluate the amount and patterns of missing data; and 4) check for violations of statistical assumptions for the planned analyses. If statistical assumptions are seriously violated, data transformations or more statistically robust methods will be considered. Covariates/confounders will be included in models secondarily, and their impact on the effect of the primary independent variable on the study outcomes will be evaluated. The randomness of missing data will be investigated using available information on subject characteristics to help discern patterns in the missing data, identify the possible covert missing data mechanisms, and inform the choice of the strategies to handle missing data. We will conduct logistic regression models to compare the characteristics of participants who remained in the study versus those who dropped out to determine if data are missing at random. If data are ignorably missing (i.e., not related to the outcome itself), likelihood estimation procedures, such as those in SAS PROC MIXED, GLIMMIX and NLMIXED as well as Mplus, will produce unbiased estimates while allowing us to retain cases with missing values on the outcome variables. If needed, multiple imputation would be used to impute missing values on the predictor variables. If data are not ignorably missing (i.e., non-randomly missing), we may use pattern mixture modeling to account for informative attrition.

Analysis Strategies for Aims 1 and 2: To examine the efficacy of the remotely-delivered AME intervention relative to the attention control on breastfeeding outcomes during hospitalization to the first two weeks postpartum (short-term; Aim 1) and up to the first 12 months (long-term; Aim 2) among overweight and obese (BMI \geq 25) women, an intent-to-treat (ITT) approach will be used, where all participants will be included in analyses as randomized, regardless of protocol adherence/deviations, treatment received, or withdrawal. Adherence to the assigned intervention, however, will be monitored, and the sensitivity of the results under the ITT model will be explored to identify the effects of the amount of intervention received (e.g., number of AME study visits) and deviations in protocol on outcomes.

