distribution will be considered with an identity link to the linear predictors. Random effects for participants will also be included. Fixed and/or time-dependent covariates (e.g., pre-pregnancy BMI category [25.0-29.9; 3034.9; 35-39.9; 40+]) may be included secondarily to adjust for group imbalances or variables related to the dependent variables based on the literature or data screening results. Standard fit criteria (e.g., AIC and BIC) also will be used to identify the best-fitting repeated measures covariance structure. F-tests will test the main and interaction effects included in the model. Individual regression parameters will be estimated with confidence intervals. For each model, residual analyses will be conducted to identify sources of model misspecification, outliers, and influential observations. Sensitivity analyses will be performed to discern the impact of influential cases on modeling results. Linear contrasts will be specified in the repeated measures models to test whether the AME intervention demonstrates greater improvements in breastfeeding outcomes compared to the attention control at each time point, in particular, when conducting hypothesis testing on the primary short-term outcomes. Point and interval estimates will be obtained for each of the comparisons examined.

For event history type outcomes (e.g., breastfeeding duration, days to the onset of lactogenesis II, days to any formula) Cox proportional hazards regression methods will be applied to allow for possible censoring of the event of interest and inclusion of the fixed and time-dependent predictors. For summary outcomes (e.g., proportion of breast milk in-hospital), generalized linear modeling will be applied.

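### A completer/dropout comparison cannot decide whether data are missing at random, and the only MNAR analysis hangs on it and is optional

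*Combined protocol and SAP*

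**What the plan says.** The missing-data strategy is under Statistical Methods, Preliminary Analyses. Observed subject characteristics will be examined to "inform the choice of the strategies to handle missing data", and logistic regression will "compare the characteristics of participants who remained in the study versus those who dropped out to determine if data are missing at random".

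Two branches follow:
- **Ignorable.** The condition reads "If data are ignorably missing (i.e., not related to the outcome itself". Likelihood procedures then "will produce unbiased estimates while allowing us to retain cases with missing values on the outcome variables". Multiple imputation is mentioned for predictors only, if needed.
- **Not ignorable.** Here "we may use pattern mixture modeling to account for informative attrition". No delta, identifying assumption or target outcome is given.

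Under Analysis Strategies for Aims 1 and 2, two further sensitivity analyses appear. In one, "the sensitivity of the results under the ITT model will be explored to identify the effects of the amount of intervention received", together with protocol deviations. The other reads "Sensitivity analyses will be performed to discern the impact of influential cases on modeling results". Neither concerns missing outcomes. The repeated-measures model is a generalized linear mixed model, for which "Random effects for participants will also be included".

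**The concern.** The plan's own definition of ignorability turns on the outcome, yet its test uses only observed characteristics. Such a comparison can give evidence against data being missing completely at random and can suggest covariates. It cannot separate MAR from MNAR. A null result is no evidence of MAR, and a positive result does not point to MNAR.

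This matters because two primary outcomes are feeding measures and the third is breastfeeding self-efficacy. Follow-up is by postpartum survey, and week 2 is the first. Whether a mother answers may depend on how feeding is going, and that dependence may differ by arm. A woman who returns no postpartum survey adds nothing to the likelihood for the 2-week feeding outcomes. A woman who misses week 2 but answers later does contribute through the mixed model, but only under MAR.

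If the check finds nothing, the plan ends with one likelihood estimate described as unbiased, and nothing shows how far it depends on MAR.

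**Working it through.** **Inputs from Sample Size and Power.** Reference exclusivity .27; test-wise level .0167 (taken as two-sided, critical z = 2.39); 105 per group analysable; 280 enrolled, so 140 per arm; about 25% combined study attrition and intervention dropout. The plan's enrolment reproduces: 210/(1 − .25) = 280. Because the 25% includes intervention dropout, it is an upper value for missing outcomes, so 10% and 15% are shown too. All odds ratios, missing rates and persistence rates below are assumptions.

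**(a) Bias and false positives with no true effect.** Let *a* and *b* be the dropout probabilities of exclusive and non-exclusive mothers, with odds ratio OR (*b* against *a*) and .27*a* + .73*b* equal to the missing rate. Then

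observed rate = .27(1 − a) / [.27(1 − a) + .73(1 − b)].

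Example, 25% missing and OR 3: a = .123, b = .297, so the observed rate is .2368/(.2368 + .5132) = .316, a bias of +.046. Rejection rates come from exact binomial enumeration of the likelihood-ratio chi-square with 105, 119 and 126 per arm. With no dependence the rate is 1.7%.

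| Missing | AME arm only, OR 2 to 5 | Rejection | Both arms (OR 3 AME, OR 2 control) | Rejection |
|---|---|---|---|---|
| 10% | +.012 to +.022 | 1.9% to 2.5% | +.005 | 1.7% |
| 15% | +.018 to +.034 | 2.3% to 3.7% | +.008 | 1.8% |
| 25% | +.031 to +.060 | 3.2% to 7.6% | +.015 | 2.0% |

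Dependence in the control arm only gives the same sizes with the opposite sign. Equal dependence gives no bias.

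**(b) What later surveys recover.** A saturated week-2 by week-6 likelihood was fitted under MAR (EM, large sample), with 25% missing and OR 3 in AME only. Week-6 exclusivity was assumed to be .75 if exclusive at week 2 and .05 if not. The +.046 becomes +.032 if half of those missing week 2 answer week 6, and +.021 if all do. Varying persistence from .85/.02 to .75/.15 gives +.026 to +.037 and +.012 to +.030. The bias shrinks but remains.

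**(c) What the check detects.** Each case had 3,000 simulated trials of 280 women, with a 5% likelihood-ratio test of dropout on arm plus three baseline variables.
- MNAR in the AME arm, bias +.016 to +.060: flagged in 5% to 8% of trials, whether each variable predicted exclusivity at OR 1.3 or 2.0 per SD.
- MAR on one baseline variable (OR 1.5 per SD), bias about 0: flagged in 45% to 63%.

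The check is near its chance rate where there is harm, and often positive where there is none.

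**(d) Tipping point.** Missing controls are held at .27, and exclusivity among missing AME women (*pm*) is lowered. With *e* the full-arm rate, *m* the missing fraction and N = 140,

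variance per arm = e(1 − e)/N + m²·pm(1 − pm)·(1/n_obs + 1/n_mis).

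The plan gives its detectable effect as both .172 and OR 2.55. From .27, OR 2.55 is odds 2.55 × .27/.73 = .943, a rate of .485. Adding .172 gives .442. Both are shown; .485 is the one that has 80% power with 105 per arm.

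- **Observed .485, 25% missing.** z starts at 3.30. At pm = .23, e = .75 × .485 + .25 × .23 = .421, the difference is .151, the variances are .00216 + .00188, and z = .151/.0636 = 2.38. Significance is lost.
- **Observed .485, 15% or 10% missing.** It never tips. With no missing AME woman exclusive, z = 2.44 and 2.89.
- **Observed .442.** It tips at pm = .37, .26 and .11 for 25%, 15% and 10% missing. At 25% missing it starts at z = 2.65, already near the threshold.

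**The case against.** The plan does recognise informative attrition and names a method for it. Its claim of unbiasedness is conditional on ignorability, and as such is broadly right. The attention control, phone or clinic follow-up of non-responders and the mixed model all lower the risk.

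The larger figures also stack assumptions: dependence in one arm only, odds ratios up to 5, and 25% missing. Under intention to treat, women who stop the intervention but answer the survey are not missing. With dependence in both arms, rejection stays at 1.7% to 2.0%. The .442 case sits close to significance, so it tips easily. At .485 the result changes only at 25% missing, and only if missing AME women do slightly worse than controls. That threshold depends on method: a plain fill-in without imputation variance moves it from .23 to about .155.

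The check could also be richer than three baseline variables, since in-hospital feeding is collected from the medical record. Adding such an indicator (assumed sensitivity .90 to .95 and specificity .60 to .80 for 2-week exclusivity) gives flags of about 5% to 14% under AME-only MNAR, or up to about 26% with an arm interaction.

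These points stand as limits on size. None gives the plan a committed MNAR analysis, and detection stays poor where bias is present.

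**Conclusion.** The concern holds. The stated decision rule cannot do what it is meant to do, and the only MNAR analysis sits behind it and is optional. The consequence ranges from negligible (equal dependence, or 10% missing) to a false difference of +.060 with a 7.6% false-positive rate (25% missing, OR 5, AME arm only, before any recovery from later surveys). For an observed rate of .485, the conclusion is at risk only near 25% missing. These sizes rest on assumed dropout mechanisms, and the direction of any bias is unknown. The primary analysis itself can stand. What is missing is a committed test of its dependence on MAR, and the plan should add one.

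**What to change.** 1. Keep the completer/dropout comparison as description and as a guide to covariates, and remove its role in deciding the mechanism.
2. Replace the optional pattern-mixture sentence with a commitment, made whatever the comparison shows, to a delta-adjusted (pattern-mixture or tipping-point) sensitivity analysis of the three 2-week primary outcomes, with delta allowed to differ by arm. Choose and justify the delta range in advance.
3. Optionally, as support and not as a substitute, impute missing 2-week outcomes using arm, BMI stratum and in-hospital feeding from the medical record.

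The cost is SAP wording and modest extra analysis. No new data are needed.
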